6.4. Subset Analyses

[Table 10](#) summarizes the defined subgroup analyses. Additional subset analyses (not defined here) may also be performed if deemed necessary. Immunogenicity testing may be performed on subsets of participants if needed prior to testing on all study participants and may be reported separately.

Table 10. Subgroup Analysis for Infant Participants

Subgroup	Endpoints	Population
GA at the time of vaccination (≥ 24 to < 28 weeks, ≥ 28 to < 32 weeks, ≥ 32 to ≤ 36 weeks)	
 Primary efficacy endpoints Immunogenicity endpoints Hospitalization due to RSV (up to 730 days) 	
 Evaluable efficacy – infant Evaluable immunogenicity – infant Evaluable efficacy – infant
Time from vaccination to delivery		
≤ 14 Days > 14 Days and ≤ 30 days > 30 Days	
 Immunogenicity endpoints 	
 ITT immunogenicity – maternal/infant
Country	
 Primary efficacy endpoints Immunogenicity endpoints Pregnancy & birth outcome Hospitalization due to RSV (up to 730 days) 	
 Evaluable efficacy – infant Evaluable immunogenicity – infant Safety – maternal/infant Evaluable efficacy – infant
Country subcategories (level of income) ⁴	
 Primary efficacy endpoints Immunogenicity endpoints Pregnancy & birth outcome Hospitalization due to RSV (up to 730 days) 	
 Evaluable efficacy – infant Evaluable immunogenicity – infant Safety – maternal/infant Evaluable efficacy – infant
Demographic risk factors		
Breastfeeding (exclusivity and duration)	
 Primary and secondary efficacy endpoints 	
 Evaluable efficacy – infant
Maternal smoking (smoker [current]/nonsmoker)	
 Primary and secondary efficacy endpoints 	
 Evaluable efficacy – infant
Number of household members	
 Primary and secondary efficacy endpoints 	
 Evaluable efficacy – infant
Infants who received palivizumab (yes/no)	
 Primary and secondary efficacy endpoints 	
 ITT efficacy – infant
Duration of planned follow-up (12 or 24 months)	
 Demographics 	
 Safety – infant
Age at vaccination: < 18 years/ ≥ 18 years	
 Safety endpoints Immunogenicity endpoints Primary and secondary efficacy endpoints 	
 Safety – maternal/infant Evaluable immunogenicity – maternal/infant Evaluable efficacy – infant
Gender	
 Safety endpoints 	
 Safety – infant
Race	
 Safety endpoints 	
 Safety – maternal/infant

Abbreviation: GA = gestational age; RSV = respiratory syncytial virus.

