2.2. Study Design

This is a Phase 3, multicenter, randomized, double-blinded, placebo-controlled study to assess the efficacy, safety, and immunogenicity of bivalent RSVpreF or placebo (1:1 randomization) in infants born to healthy women vaccinated during pregnancy, and the safety and immunogenicity in the pregnant women. This will be a global study, including sites in both the northern and southern hemispheres, and it will span multiple RSV seasons.

This is an event-driven study with a target of 124 adjudicated (primary-endpoint) cases of MA-LRTI due to RSV (meeting the case definition in the per-protocol infant population described in [Section 9.2 of the protocol](#)). Vaccination of maternal participants will occur at a time of year such that the infant is likely to be exposed to seasonal RSV during the first 6 months of life. It was anticipated that approximately 6900 mother-infant pairs would be needed to accumulate 124 per-protocol cases prior to the global COVID-19 pandemic. With the variable RSV season, the sample size may need to be increased and enrollment could go up to 10,000 maternal participants based on the number of RSV cases.

Study-eligible pregnant women will be randomized in a 1:1 ratio to receive a single dose RSVpreF or placebo. The dose of RSV prefusion F antigen in RSVpreF for this study will be 120 µg (60 µg A and 60 µg B).

Assessments for mothers will include parameters to allow descriptions of safety, tolerability, and immunogenicity of the vaccine in maternal participants.

For all infant participants, data will be collected for any medically attended respiratory illness to assess for cases of LRTI due to RSV (efficacy endpoint). Additionally, throughout the study all respiratory illnesses, SAEs, and NDCMCs reported will be assessed in this population. Infant participants enrolled during the first year of the study will be followed up for 24 months after birth, to include longer-term RTI surveillance and safety oversight to address safety and the possibility of conferred enhanced protection (antibody persistence) during a second RSV season. All other infants will be followed up for 12 months after birth. All MA-RTIs meeting the protocol definition for a potential study endpoint will be adjudicated by an independent EAC. In addition, this study will use an E-DMC to monitor vaccine safety and efficacy and study futility.

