3.3. Other Endpoints

3.3.1. Exploratory Endpoints – Infant Participants

- RSV-positive MA-RTI (as confirmed by the EAC) occurring within 90 days, 120 days, 150 days, and 180 days after birth.
- RSV-positive MA-RTI occurring 181 to 730 days after birth.
- Incidence of all-cause MA-RTIs up to 730 days after birth.
- MA-LRTIs due to RSV occurring 361 to 730 days after birth.

- Severe MA-LRTIs due to RSV occurring 181 to 730 days after birth (as confirmed by the EAC).
- Hospitalization due to RSV occurring 181 to 730 days after birth (as confirmed by the EAC).
- MA-LRTIs due to any cause occurring 181 to 730 days after birth.
- RSV subgroup A– and subgroup B–specific MA-LRTI.
- Positivity for non-RSV respiratory pathogens obtained at unplanned MA-RTI visits.
- RSV A and RSV B serum neutralizing titers measured at birth.
- Primary and secondary efficacy by select demographic risk factors (eg, breastfeeding, maternal smoking, number of household members).
- Univariate summaries of healthcare utilization variables, which may include the following: number and type of medical visits, length of hospital stay, requirement for mechanical ventilation, requirement for respiratory diagnostic procedures, requirement for IV fluids, requirement for prescriptions, and antibiotic use.
- IgG concentrations against prefusion F measured at birth.
- MA-RTI, MA-LRTI, and severe MA-LRTI due to RSV occurring 0 to 730 days after birth in premature infants <37 weeks of age.

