3.4. Baseline Variables

3.4.1. Baseline Variables – Infant Participants

Day 1 is defined as the day of birth (Visit 1) for the infant participants.

Day 1 is considered the baseline visit for the following assessments in infant participants: immunogenicity (cord blood sample collected at birth), physical examination, and vital signs.

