5.2.1. Analyses for Binary Endpoints

The number and percentage of participants in each category will be summarized. The 95% CI for percentage, and for the difference in percentages, will also be presented, where appropriate.

The analysis of efficacy will use a conditional exact test¹ based on the binomial distribution of the number of disease cases in the RSV vaccine group, given the total number of cases in both groups. The number of cases $x_i \sim P(\lambda_i)$, where $P()$ is the Poisson distribution ($i = 1$ denotes placebo, $i = 2$ denotes vaccine). It is known that $x_2|T = t \sim B(T, \pi)$, where $B()$ is the binomial distribution, $T = x_1 + x_2$ (the total number of events), and $\pi = \lambda_2 / (\lambda_1 + \lambda_2)$. Then, assuming equal numbers of participants per group, testing the hypothesis $H_0: VE \leq \theta$ is equivalent to testing $H_0: \pi \geq (1 - \theta) / (2 - \theta)$.

The 95% CI for proportions will be constructed by the Clopper-Pearson method described by Newcombe.² The 95% CI will be presented in terms of percentage.

The 95% CI for differences in the proportions will be computed using the Miettinen and Nurminen method.³ The 95% CI will be presented in terms of percentage.

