5.4. Endpoint Events and Definitions

5.4.1. Endpoint Events and Definitions – Infant Participants

The study endpoints for infant participants employ the event definitions in Table 8.

Table 8. Primary and Secondary Endpoint Events and Definitions in Infant Participants

Study Endpoint/Assessment	Study Definition
Medically attended visit	Infant participant has been taken to or seen by a healthcare provider (eg, outpatient or inpatient visit, emergency room, urgent care, or home visit).
MA-RTI visit for infant participant	A medically attended visit AND 1 or more of the following RTI signs and symptoms: 
 • Nasal discharge for 24 hours or more • Difficulty breathing, labored breathing, or rapid breathing for any duration • Cough • Inability to feed for any duration because of respiratory symptoms • Apnea • Any other respiratory symptom of concern
RSV-positive test ^a	
 • RSV RT-PCR–positive test result by Pfizer central laboratory OR • RSV-positive test result by certified^b laboratory with NAAT for RSV
MA-RTI due to RSV ^a	
 • An MA-RTI visit AND • RSV-positive test result as described in Section 8.1.1.1 of the protocol
MA-LRTI due to any cause	
 • Infant with an MA-RTI visit AND • Fast breathing (respiratory rate \geq60 bpm for <2 months of age [<60 days of age], \geq50 bpm for \geq2 months to < 12 months of age, or \geq40 bpm for \geq12 months to 24 months of age) OR • SpO₂ <95% OR • Chest wall indrawing

Table 8. Primary and Secondary Endpoint Events and Definitions in Infant Participants

Study Endpoint/Assessment	Study Definition
MA-LRTI due to RSV ^a	
 • Infant with an MA-RTI visit AND • Fast breathing (respiratory rate ≥ 60 bpm for <2 months of age [<60 days of age], ≥ 50 bpm for ≥ 2 months to < 12 months of age, or ≥ 40 bpm for ≥ 12 months to 24 months of age) OR • SpO₂ <95% OR • Chest wall indrawing AND • RSV-positive test result as described in Section 8.1.1.1 of the protocol
Hospitalized RTI due to RSV ^a	
 • An RTI due to RSV that results in hospitalization

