6.1.1.1.1. Main Analysis

- Estimand strategy: Hypothetical.
- Analysis set: Evaluable efficacy – infant ([Section 4](#)).
- Analysis methodology: VE will be analyzed using a conditional exact test based on the binomial distribution of the number of disease cases in the RSV vaccine group, given the total number of cases in both groups.
- Intercurrent events and missing data: All postdiscontinuation or postviolation observations will be censored; such events include the infant receiving palivizumab or another monoclonal antibody targeting RSV and the infant receiving transfusions of more than 20 mL/kg of any blood products at ≤ 180 days of age.
- For each group, the number (n), percentage, and 95% CI of RSV-positive MA-LRTI cases occurring within 90 days, 120 days, 150 days, and 180 days after birth, as confirmed by the EAC, will be presented for each group. Severe MA-LRTI cases are a subset of MA-LRTI cases, and all severe MA-LRTI cases will also be considered MA-LRTI cases.

- VE compared to placebo along with the corresponding 100(1- alpha)% CI (adjusted for the interim) will be presented. This will be based on raw numbers of cases and also with an adjustment for any differences in follow-up time. See [Section 5.1](#) for testing procedures.
- Kaplan-Meier curves showing accrual of cases for this endpoint over 180 days will be presented.

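### VE by breastfeeding duration groups infants on something RSV illness can shorten; if shortening differs by arm, or VE changes with age, subgroup VEs can differ without effect modification

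*SAP*

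**What the plan says.** Section 3.3.1 makes this an exploratory infant endpoint: "Primary and secondary efficacy by select demographic risk factors (eg, breastfeeding, maternal smoking, number of household members". Table 10 in Section 6.4 carries it out. Under demographic risk factors it lists "Breastfeeding (exclusivity and duration", for the primary and secondary efficacy endpoints in the evaluable efficacy infant set. The row gives no cut-points, no age at which feeding is read, and no rule for an infant who falls ill before weaning. The gestational-age row in the same table does have cut-points, and the maternal-smoking row has status categories.

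Four other places bear on the point:

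- Section 3.4.1 sets the infant baseline: "Day 1 is defined as the day of birth (Visit 1) for the infant participants". Duration of breastfeeding is therefore a post-baseline variable.
- Table 8 (Section 5.4.1) includes among the qualifying respiratory signs "Inability to feed for any duration because of respiratory symptoms".
- Section 5.2.1 bases VE on the split of cases between arms, "assuming equal numbers of participants per group".
- Section 6.1.1.1.1 says of the reported VE: "This will be based on raw numbers of cases and also with an adjustment for any differences in follow-up time".

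**The concern.** A subgroup comparison of VE is easiest to read when membership is settled before the outcome can occur. Total breastfeeding duration is not. An infant who becomes a case on day 30 is classified by feeding that happens after day 30, and the illness may be the reason it stopped. Such a case moves from the group it would have belonged to (longer) into the shorter one.

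The estimator works on case splits, so what matters is whether the fraction of cases moved is the same in both arms. The SAP treats severe MA-LRTI and hospitalization due to RSV as separate endpoints, so a vaccine that makes breakthrough illness milder is within what the trial sets out to examine. Milder illness could mean fewer vaccine-arm cases moved. VE that changes with age is a second route, and the SAP evaluates VE over successive intervals after birth.

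At stake is the reading of one exploratory table: an apparent effect of breastfeeding on VE could be produced partly by the illness itself.

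**Working it through.** **Method check.** The breastfeeding row carries no figure, so the estimator was checked against the two efficacy rows of Table 11. VE = 1 − (vaccine cases / placebo cases). The limits are Clopper-Pearson limits for π, converted by 1 − π/(1 − π), at half the 1-sided alpha.

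- 14 against 48 cases, 1-sided 0.075%: 70.8% (25.4%, 90.5%). The SAP prints 71% (25%, 91%).
- 6 against 37 cases, 1-sided 0.007%: 83.8% (27.2%, 98.3%). The SAP prints 84% (27%, 98%).

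**Inputs from the SAP.** Section 2.2 gives the allocation ("Study-eligible pregnant women will be randomized in a 1:1 ratio") and the planned size ("approximately 6900 mother-infant pairs would be needed to accumulate 124 per-protocol cases"). That is 3450 infants per arm. Section 7.2 gives the design VE of 60%. Placebo risk p solves 124 = 3450 × p × (1 + 0.4), so p = 124/4830 = 2.57%. This gives 88.6 placebo and 35.4 vaccine cases.

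**Assumptions (the SAP has no figures for these).** True VE is 60% in every infant. Half of infants would naturally be in the longer-duration group, so each group starts with 44.3 placebo and 17.7 vaccine cases. A fraction qP of placebo cases and qV of vaccine cases in the longer group moves to the shorter group because of illness.

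At an even split:

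- VE(long) = 1 − 0.4 × (1 − qV)/(1 − qP)
- VE(short) = 1 − 0.4 × (1 + qV)/(1 + qP)

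| qP | qV | VE long | VE short | Gap (points) |
|---|---|---|---|---|
| 0 | 0 | 60.0% | 60.0% | 0 |
| 30% | 30% | 60.0% | 60.0% | 0 |
| 50% | 50% | 60.0% | 60.0% | 0 |
| 25% | 17.5% | 56.0% | 62.4% | 6.4 |
| 30% | 20% | 54.3% | 63.1% | 8.8 |
| 40% | 20% | 46.7% | 65.7% | 19.0 |
| 20% | 30% | 65.0% | 56.7% | 8.3, reversed |

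Worked line for 30% against 20%: the long group has 14.2 vaccine and 31.0 placebo cases, the short group 21.3 and 57.6.

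Dividing by the number of infants in each group barely changes the equal-shift result, because the event is rare: 60.2% long against 59.8% short at 30%, and 60.3% against 59.7% at 50%.

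**Age-varying VE with equal shifts.** Assume VE of 70% to day 90 and 50% after it in every infant, half the placebo cases in each period (so 60% overall), and duration cut at 90 days. Only early cases can move, because an infant who weans after a late case has already passed 90 days.

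- q = 30%: short = 1 − (0.15 + 0.25 + 0.045)/1.15 = 61.3%; long = 1 − (0.105 + 0.25)/0.85 = 58.2%. Gap 3.1 points.
- q = 50%: short = 1 − 0.475/1.25 = 62.0%; long = 1 − 0.325/0.75 = 56.7%. Gap 5.3 points.

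**Scale of noise.** A subgroup with 62 cases split 18 against 44 has VE 59.1% with a 95% CI of 27.7% to 77.8%.

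**The case against.** The strongest reply is that shortening alone does no harm. That is right: with equal shortening and constant VE, both subgroups return the overall VE. A reader might infer that any illness-related weaning biases this table, and the calculation does not support that. The distortion needs a difference between arms or a change in VE with age. The SAP gives no figure for either, and an inability to feed of any duration need not mean permanent weaning.

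A reader might also construct a much larger gap. With 100 placebo and 40 vaccine cases, putting 60% of placebo and 40% of vaccine cases in the short group gives 1 − 16/60 = 73% against 1 − 24/40 = 40%. If illness can only shorten feeding, this requires a natural short share of at most 40%. At exactly 40%, one third of the otherwise long-fed placebo cases would have to move and no vaccine case could. At an even split it is impossible. It should not be used as a typical size.

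Two further inferences go beyond the text. The SAP does not say when exclusivity is recorded, so it cannot be said to be known only after follow-up; if it is fixed at birth, the problem does not arise for it. Nor does the SAP call breastfeeding a baseline variable: Table 10 also groups by infant palivizumab receipt, and no interaction test is stated for the breastfeeding row.

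Finally, Section 2 says programming rules are prepared separately, and the protocol may define how feeding is collected. That may supply cut-points, but cut-points for total duration would not stop the illness from deciding which side of the cut an infant falls on. This part of the concern stands.

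**Conclusion.** The concern holds for duration, in conditional form. As written, the row can show different VEs by breastfeeding duration when none exist, if illness-related shortening differs by arm or VE changes with age. Under the assumed arm-differential rates and an even natural split the gap is about 6 to 19 points. Under equal shifts with the assumed fall in VE at day 90 it is about 3 to 5 points. Without either condition it is essentially nil. The direction is not fixed: it reverses if vaccine-arm cases wean more often. Many of these gaps would lie within the sampling error of a subgroup of this size.

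This is a small improvement to an exploratory table. No primary or secondary test depends on it.

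**What to change.** In Table 10, drop total breastfeeding duration as a grouping variable for VE. Group by feeding status (exclusive, partial, none) at birth, or at a fixed early landmark such as 1 month with only later cases and person-time counted. Choose whichever time point the trial already records. Section 3.5.3.2 shows an assessment at 1 month but does not say that feeding is recorded there, so this needs confirming first. Apply the same rule to exclusivity unless it is fixed at birth.

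If the feeding data exist, the cost is a change of SAP wording. The downside of a 1-month landmark is that first-month cases drop out of this table, about a third of the 90-day window. Grouping by status at birth avoids that loss.

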6.5. Baseline and Other Summaries and Analyses

6.5.1. Baseline Summaries

6.5.1.1. Baseline Summaries for Maternal Participants

For each group, descriptive summary statistics for demographic characteristics (age at vaccination, sex, race, and ethnicity; in addition, GA at vaccination will be presented for the following groups: ≥ 24 and < 28 weeks, ≥ 28 to < 32 weeks, and ≥ 32 to ≤ 36 weeks, and > 36 weeks), current/former substance use, and obstetric history as described in [Section 3.5.4](#) will be generated for each group based on the maternal safety population.

The number and proportion of participants with at least 1 medical history PT, arranged by SOC, will be tabulated for each group. The medical history summary is based on the maternal safety population.

Participant data listings for demography and baseline characteristics data will also be generated.

6.5.1.2. Baseline Summaries for Infant Participants

Descriptive summary statistics for demographic characteristics will be generated by vaccine group based on the infant safety population.

Participant data listings for demography and other infant data will also be generated.

6.5.2. Study Conduct and Participant Disposition

The number and proportion of randomized participants will be included in the participant disposition summary. In addition, participants who completed the delivery visit, those who withdrew before delivery, along with the reasons for withdrawal, those who completed the follow-up visit, and those who withdrew before the follow-up visit, along with the reasons for withdrawal, will be tabulated by vaccine group separately for maternal and infant participants. The reasons for withdrawal will be those as specified in the database. Information regarding additional informed consent from a legally authorized representative if a mother cannot provide informed consent, will be listed. This will be created only for infants.

Participant disposition tables will be generated separately for maternal and infant participants.

Participants excluded from the evaluable efficacy – infant, evaluable immunogenicity (maternal and infant), mITT efficacy – infant, and mITT immunogenicity (maternal and infant) populations will also be summarized with reasons for exclusion. These summaries will be generated separately for maternal and infant participants.

The numbers and percentage of participants who were randomized, were vaccinated, and had blood drawn within the protocol-specified time frame, and outside the specified window, will be tabulated by vaccine group. These summaries will be generated separately for maternal and infant participants.

The numbers and proportions of participants with e-diary data not transmitted, transmitted by day (Days 1-7), and transmitted on “all days” will be summarized by vaccine group. These summaries will be generated only for maternal participants.

Data listings for participants who withdrew during the study will be generated. In addition, data listings for participants excluded from different populations will be generated separately. These listings will be generated separately for maternal and infant participants.

The important protocol deviations listings will be generated separately for maternal and infant participants.

6.5.3. Concomitant Medications and Nondrug Treatments

Nonstudy vaccines and medications taken during pregnancy or during the study will be categorized according to the WHO Drug Dictionary and summarized in accordance with the sponsor reporting standards. These will be generated (if needed) separately for maternal and infant participants.

MA-RTI concomitant medications and antibiotic medications associated with an MA-RTI event may be summarized separately (antibiotics will be identified based on ATC4 category in the database and confirmed by Pfizer clinical personnel on an ongoing basis). These summaries will be generated separately for maternal and infant participants.

6.6. Safety Summaries and Analyses

6.6.1. Adverse Events

It should be recognized that most studies are not designed to reliably demonstrate a causal relationship between the use of a pharmaceutical product and an AE or a group of AEs. As such, safety analysis is generally considered as an exploratory analysis and its purpose is to generate hypotheses for further investigation. The 3-tier approach facilitates this exploratory analysis. There will be no adjustment for multiple comparison in the analyses.

Analyses and summaries of primary AE endpoints using the 3-tier approach are described in detail in [Section 6.1.2](#) and [Section 6.1.3](#).

In addition, another summary will be created to present AEs of special interest (as defined in the protocol and SAP).

Listings of participants reporting any AE and immediate AEs, and listings of all reported AEs will be generated. In addition, AEs occurring after participants signed the informed consent and prior to vaccination will also be listed. Listings of medical device related AEs will be generated only for maternal participants.

All summaries and listings for the AEs will be generated separately for maternal and infant participants.

